7.2 Exclusion Criteria

- 1.) Primary home facility not KP Santa Rosa, Santa Clara, Oakland, San Francisco, or San Rafael Medical Centers
- 2.) Interpreter needed
- 3.) Admitted from skilled nursing facility/nursing home
- 4.) Homeless
- 5.) Residence outside MTMs provider delivery area
- 6.) Prior history of organ transplant

7.3 Electronic Screening

Patients at the KP Santa Rosa, Santa Clara, Oakland, San Francisco, and San Rafael Medical Centers will be identified daily for eligibility criteria using the KPNC EHR and associated data systems. A cron job scheduled on the KPNC DOR SAS grid server will execute a SAS statistical software program at 6:45 AM Monday through Friday that pulls relevant data from EHR databases, automatically applies the inclusion and exclusion criteria, randomizes patients to one of the three study arms, generates a unique study identifier, and outputs a file of all patients hospitalized at the participating KPNC hospital and their associated information needed for recruitment that is then automatically uploaded to web-based study tracking systems based at the KPNC DOR.

7.4 Randomization

This study will incorporate the concept of pre-randomization (i.e., prior to obtaining informed consent and administering the intervention) in order to streamline the study workflow consistent with the pragmatic trial design. Pre-randomization will be stratified by participating KPNC medical center (i.e. participants will be pre-randomized separately within each medical center).

7.5 Manual Eligibility Confirmation

After automated identification and randomization, a list of initially eligible patients will be uploaded to a KPNC DOR-hosted website that only KPNC DOR research staff will have access to for the purpose of this study. KPNC DOR research staff will complete manual review of patient EHR data to confirm study eligibility before contacting study participants. The additional exclusion criteria that were identified through manual review of EHR data includes:

- 1) Planned discharge to a skilled nursing facility, nursing home, rehabilitation facility, assisted living facility, board and care facility, or hospice facilities
- 2) Planned receipt of home hospice or comfort care services upon discharge
- 3) CKD progression to eGFR <30 mL/min/1.73 m² before discharge
- 4) Died during the index hospitalization
- 5) Inability to provide informed consent (e.g., due to acute delirium or dementia, substance use disorder, speech or hearing disability, significant language barrier)
- 6) Inability to receive meals (e.g., dietary restrictions, residence outside delivery areas by MTMs vendors, or already receiving meals from another meal service)
- 7) A study physician deemed not a suitable candidate due to severe multimorbidity or other life-limiting diagnoses

8 Follow-up

KPNC DOR research staff will check enrolled participants' bed status daily for discharge and track each participant's status in the Appian-based study online tracking system. KPNC DOR research staff will place a note in the Appian-based study online tracking system the date that participants are discharged from the hospital.

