Participants at the KP Santa Rosa, Santa Clara, Oakland, San Francisco, and San Rafael Medical Centers will be identified daily from EHR data and electronically screened for inclusion criteria using KPNC EHR and associated data systems. After identification, participants will be pre-randomized to intervention or usual care arms using a SAS statistical software randomization program, and a list of initially eligible patients will be uploaded to a KPNC DOR-hosted web application to which only KPNC DOR research staff will have access. After confirming eligibility through manual review of the EHR, KPNC DOR research staff will then call the participant by phone in their hospital room and inquire about their interest in learning about the KP NOURISH Study. If interested, KPNC DOR research staff will review the procedures that the participant would be asked to complete and review verbal consent. Participants providing verbal consent to participate in the study will also be asked for verbal Health Insurance Portability and Accountability Act (HIPAA) Privacy Rule Authorization. Participants providing verbal consent and HIPAA Privacy Rule Authorization will then complete the baseline study visit during the enrollment phone call, which includes questions about sociodemographic characteristics, selected patient reported outcomes, contact information, and ability to receive MTMs (if randomized to receive MTMs). Additionally, following enrollment, KPNC DOR research staff will email the participant thanking them for agreeing to participate in the study and to provide contact information for the study team and for the KPNC Institutional Review Board (IRB) if they have any questions after completing the baseline study visit. This email will also include a study flyer with additional details about their participation in the study. Participants requesting a study mailing will also be mailed the thank you letter and study flyer to their home residence.

After completion of the baseline study visit, KPNC DOR research staff will monitor the participant's discharge status on a daily basis, and upon discharge notify the MTMs service provider (Ceres or POH) to begin delivery service for up to 10 weeks for participants assigned to MTMs alone or and to MTMs with remotely delivered nutritional counseling groups. Participants assigned to the usual care group will be passively

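### The arm is assigned before manual eligibility review and consent, the documents describe no concealment of it, and only consenting patients are analysed, so entry to the primary comparison could differ by arm

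*Protocol*

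**What the plan says.** **Assignment.** Protocol 7.3 describes a weekday program that "automatically applies the inclusion and exclusion criteria, randomizes patients to one of the three study arms". Section 7.4 presents this as a deliberate choice: "pre-randomization (i.e., prior to obtaining informed consent and administering the intervention) in order to streamline the study workflow". The Schedule of Assessments agrees, with randomization on day 0 and consent on day 1.

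**Manual review.** Section 7.5: "After automated identification and randomization, a list of initially eligible patients will be uploaded to a KPNC DOR-hosted website". Then: "KPNC DOR research staff will complete manual review of patient EHR data to confirm study eligibility before contacting study participants". The exclusions applied at this step include inability to consent, inability to receive meals, and "A study physician deemed not a suitable candidate due to severe multimorbidity or other life-limiting diagnoses".

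**Consent call.** Under Section 6, the research staff who confirm eligibility then phone the patient, take verbal consent and HIPAA authorization, and run the baseline visit in the same call. One baseline item is "ability to receive MTMs (if randomized to receive MTMs".

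**Analysis set.** SAP 3.1 limits the primary population to patients who were randomized, gave consent and left hospital alive, and analyses them as randomized under the intention-to-treat label.

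**Adjustment.** SAP 3.3 and 4.1 adjust the Cox model for acute severity, predicted readmission risk, multimorbidity, active Covid-19 and any observed baseline differences.

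**The concern.** Random assignment protects the comparison only if what happens between assignment and entry to the analysis set does not depend on the arm. Here two filters sit in that interval: a chart review with some discretionary grounds, and the patient's decision on consent. Both are handled by one staff group, and no step in the documents keeps the arm from that group.

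If doubtful or sicker patients are excluded more readily in one arm, or if willingness to join differs by arm, the groups differ before any meal is delivered. Such patients leave the primary analysis altogether, so analysing the remainder as randomized does not restore the balance. What is exposed is the primary hazard ratio for 90-day readmission.

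**Working it through.** **Step 1: what the text shows about the arm.**

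| Step | Where | Is the arm known to staff? |
|---|---|---|
| Automated screening and randomization | 7.3, 7.4 | Arm created here |
| List uploaded for research staff | 6, 7.3, 7.5 | Not stated |
| Chart review and exclusions | 7.5 | Not stated |
| Consent and HIPAA authorization | 6, 11.3 | Not stated |
| Baseline questions, same call | 6 | Needed, because one item depends on the arm |
| Primary analysis | SAP 3.1 | Only consenting patients discharged alive |

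The one sentence on treatment-revealing data (Protocol 11.4.3) concerns the final database, not screening or consent.

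**Step 2: a related contradiction.** Section 7.5 item 6 excludes patients who cannot receive meals. Section 6 says patients assigned to MTMs who cannot receive meals are still followed passively and surveyed. Section 6 also puts the meal-ability question only to the MTMs arms. A patient of this kind could therefore be handled differently according to arm.

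**Step 3: size.** The documents give no exclusion or refusal rates by arm and do not say how many patients will be pre-randomized to enroll 2000. The bias cannot be computed, only illustrated. From SAP 2: 10% 90-day risk, 1000 per arm, two-sided alpha 0.05. All consent shares, exclusion shares and stratum risks below are assumptions. There is no true effect and no covariate adjustment.

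Formulas, with pM and pU the MTMs and usual-care risks:
- HR = ln(1 − pM) / ln(1 − pU)
- events E = 1000 × (pM + pU)
- d = ln(HR) × √E / 2
- type I error = Φ(−1.96 − d) + Φ(−1.96 + d)

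*Consent differs.* A fraction cU of usual-care patients and cM of MTMs patients consent, and the extra MTMs consenters have risk r. Then pU = 0.10 and pM = (cU × 0.10 + (cM − cU) × r) / cM. For 80% vs 60% and r = 0.15: pM = (0.06 + 0.03) / 0.80 = 0.1125; HR = 0.1193 / 0.1054 = 1.13; E = 212.5; d = 0.91; type I error about 15%.

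*Exclusion differs.* A fraction f of patients, at 25% risk, is excluded in MTMs only. Then pM = 0.10 and pU = (1 − f) × 0.10 + f × 0.25.

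| Assumed difference by arm | pM | pU | HR | Type I error |
|---|---|---|---|---|
| Consent 65% vs 60%, r = 15% | 0.1038 | 0.10 | 1.04 | about 6% |
| Consent 80% vs 60%, r = 15% | 0.1125 | 0.10 | 1.13 | about 15% |
| Consent 80% vs 60%, r = 20% | 0.125 | 0.10 | 1.27 | about 43% |
| Consent 80% vs 60%, r = 5% | 0.0875 | 0.10 | 0.87 | about 16% |
| f = 1% | 0.10 | 0.1015 | 0.98 | 5.1% |
| f = 2% | 0.10 | 0.1030 | 0.97 | 5.6% |
| f = 5% | 0.10 | 0.1075 | 0.93 | about 9% |

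**Step 4: a second model.** Let a high-risk stratum make up a share h = 20–30% of patients, with 2–3 times the risk of the rest, and let a fraction g of that stratum be lost from MTMs only. The stratum's share in MTMs becomes h(1 − g) / (1 − hg). At 10% base risk, g = 10–30% gives HR 0.99 to 0.91 and type I error 5.1% to 10.1%; g = 50% gives HR 0.92 to 0.84 and 8.7% to 22%. If the loss falls on usual care instead, the bias reverses.

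**The case against.** The case against a stronger claim is good, and most of it stands.

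- *A reader might infer that reviewers see the arm when they exclude patients.* The documents do not say so. Section 7.3 says only that the file holds the information needed for recruitment. Visibility at review is inferred from silence.
- *A reader might infer that patients learn their arm before deciding on consent.* Section 6 places the arm-dependent item after consent and authorization. It shows that the arm is needed by then, not that it was disclosed before. The consent pages are not available, so wording common to all arms may already exist.
- *A reader might infer that staff have a reason to keep doubtful patients out of the meal arms, or choose whom to phone.* The documents mention no limit on meal places, and Protocol 11.3 says eligible patients will be contacted. Nor do they say what drives acceptance of meals.
- *A reader might infer that the adjusted model is useless here.* It is not. The pre-specified indices target the sickness that a multimorbidity exclusion would act on, and every figure above is unadjusted. What remains is selection on things not in SAP Table 3-1, which lists no food insecurity, living situation or social support, and on willingness to consent.
- *The larger figures rest on a 20-point consent gap.* With a 5-point gap, or exclusion of 1–2% of patients, type I error stays at about 5–6%.

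Pre-randomization is a stated pragmatic choice, and residence outside the delivery area is already screened out automatically (7.2). Neither point answers the core difficulty: unconcealed steps after assignment, combined with an analysis set that depends on consent.

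**Conclusion.** The point holds as a gap in described concealment and in reporting, not as evidence that the trial is biased. As written, the plan lets the arm influence who enters the primary analysis, and nothing planned would show whether it did: there is no tabulation of exclusions and refusals by arm, and no analysis of all pre-randomized patients.

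Size and direction are unknown. In the illustrations the null hazard ratio moves anywhere from 0.84 to 1.27. Type I error runs from about 5–6% for small differences by arm to 15% or more for a 20-point consent gap, all under assumed inputs and before adjustment. Adjustment should reduce the part due to measured severity, but not the part due to unmeasured social need or willingness to consent.

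This should be fixed, mainly because the remedy is cheap. Confidence is moderate, since visibility of the arm before the baseline questions is inferred rather than stated.

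**What to change.** 1. Keep the automated pre-randomization. State in Protocol 6 and 7.3–7.5 that the web application releases the arm only after three things are saved: the 7.5 eligibility decision with its reason, verbal consent with HIPAA authorization, and the baseline answers.
2. Ask every patient about ability to receive meals, before release. Otherwise the arm-dependent item cannot be asked under step 1.
3. Use consent wording common to all three arms, or confirm in the protocol that this is already so.
4. Reconcile 7.5 item 6 with the Section 6 text on MTMs participants who cannot receive meals, so that the rule is the same in every arm.
5. In the SAP, plan to report by arm the numbers pre-randomized, excluded (by reason), approached and declined.
6. Where the IRB permits, add a sensitivity analysis of all pre-randomized patients using EHR outcomes. Section 6 says all identified participants are followed through the EHR, which suggests the data may exist, though it does not settle the position for people who declined. The estimate will be diluted, because patients who do not enroll get no meals, but it does not depend on who was let in.

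The cost is a display rule in an existing application, a revised script and an IRB amendment. Some patients may be disappointed to learn after consenting that they are in usual care, and a few may withdraw early. If enrollment is too far advanced for steps 1–3, steps 5 and 6 can still be done.

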8.1 Follow-up in Usual Care Participants

Following discharge from the index hospitalization, participants randomized to the usual care arm are followed passively by KPNC DOR research staff through the KPNC EHR over the course of the next 10 weeks.

8.2 Intervention Follow-up

[figure not shown]
8.2.1 10-Week MTMs Delivery

After participants assigned to the MTMs alone or MTMs plus remotely delivered nutritional counseling arms are discharged, KPNC DOR research staff will create Excel files of the discharged participants' intake information and send it to Ceres and POH staff. Ceres and POH staff will contact patients and complete intake within 24 hours of patient discharge from the hospital.

During this initial phone call, Ceres and POH staff will use a structured approach to discuss:

- The participant's health needs
- The participant's current diet
- The MTMs program

Ceres and POH will also schedule the first MTMs delivery date and the weekly delivery times. Ceres and POH will target to deliver the first MTMs within 72 hours and no later than within 1 week of hospital discharge.

Over the course of the next 10 weeks, Ceres and POH delivery drivers will conduct wellness checks to briefly assess the well-being of the participant when they deliver weekly meals. Participants will also complete meal evaluations forms for the past week's meals.

Ceres and POH will document when they are unable to complete a delivery and communicate missed deliveries to the KPNC DOR research team to try to facilitate a successful delivery attempt.

Once the last MTMs delivery is made at the end of 10 weeks, Ceres and POH will inform the KPNC DOR research team and the date of the last meal delivered will be entered into the Appian-based study online tracking system.

8.2.2 Adjustment in MTMs

Compliance with study-provided MTMs will be encouraged by KPNC DOR research staff and meals vendors at each planned contact. Participants will be allowed to pause delivery of MTMs for up to two consecutive weeks as necessary (e.g., due to trips or buildup of MTMs at home). Participants can also request to receive as few as 4 meals per eligible household member per weekly home delivery.

8.2.3 Remotely Delivered Nutritional Counseling

For participants assigned to MTMs with remotely delivered nutritional counseling, Ceres and POH will also schedule the participant's first telephone or video visit with a RDN sometime during Week 1 or Week 2 post-discharge. The RDN will conduct their second telephone or video visit with the participant during Week 4 or Week 5 and have one last visit with the participant during Week 8 or Week 9 (see overview of nutrition education content described in Table 3 below).

nutritional counseling.					
Nutrition Counseling Visit #	Completion window (post discharge)	Heart Failure	Type 2 Diabetes Mellitus	Chronic Kidney Disease	
	Week 1-2	 Review 10-week food plan Introduce education materials Review the Healthy Plate Review nutrition for heart failure Instruct on fluid restriction and teach volume concepts 	 Overview of packet Managing diabetes overview Know your carbohydrates DASH diet basics/principles MyPlate MyPlate assessment 	 Review 10-week food plan Introduce education materials Review MyPlate for CKD Review nutrition for CKD DASH diet meal plan 	
2	Week 4-5	 Check-in on goals Dietary approaches to stop hypertension (DASH) diet meal pattern Low sodium diet Label reading 	 Blood glucose tests Hypoglycemia Hyperglycemia Diabetes goals and progress Diabetes true/false 	 Check-in on goals Meal planning Reading a food label Sodium in processed foods 	

Table 3. Nutritional education content by study visit and qualifying chronic condition for participants assigned to receive MTMs with remotely delivered nutritional counseling.

Nutrition Counseling Visit #	Completion window (post discharge)	Heart Failure	Type 2 Diabetes Mellitus	Chronic Kidney Disease
3	Week 8-9	 Evaluation of goals Kitchen basics Recipe reading and use Navigate Eat Fresh (if internet access) Provide written instruction for cooking and recipes Cooking skills Grocery shopping scavenger hunt (practice with food labels) 	 Nutrition facts label Sugar shockers Cut out added sugars Rethink your drink + activity 	 Review DASH diet education Check in/review meal planning Personalized recipes Fast food choices

8.3 10-Week Study Completion Interview

For patients assigned to the usual care arm, KPNC DOR research staff will contact patients at 10-weeks after discharge from the index hospitalization. During this phone call, KPNC DOR research staff will ask patients about measures of:

- Self-efficacy
- Social isolation
- Perceived caring related to diet (i.e., perception that current meals help create a caring environment that facilitates healing)

Once participants have completed this telephone- or video-based survey, the KPNC DOR research staff will thank them for their time and inform them that they will be receiving a thank you letter and a \$10 gift card.

For patients assigned to the MTMs alone arm or the MTMs plus remotely delivered nutritional counseling arm, KPNC DOR research staff will contact patients after Ceres and POH have delivered their last meals and informed the DOR research team of the completion of MTMs service. During this telephone- or video-based survey, DOR research staff will ask patients about measures of:

- Self-efficacy
- Self-reported levels of isolation
- Perceived caring (e.g., participating in a delivered MTMs program helps create a caring environment that facilitates healing)
- Satisfaction with MTMs vendor service

Participants assigned to the MTMs plus remotely delivered nutritional counseling arm will also be asked about their satisfaction with the nutritional counseling they received. Once participants have completed the survey, KPNC DOR research staff will thank them for their time and inform them that they will receive a thank you letter soon.

9 Discontinuation/Withdrawal

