Aim 1 (Primary): To determine if MTMs provided for up to 10 weeks after hospital discharge for patients with pre-existing heart failure, diabetes mellitus or chronic kidney disease will reduce the risk of all-cause readmissions at 90 days after discharge.

Hypothesis 1: Patients receiving MTMs will have lower all-cause readmission rates at 90 days compared with patients who are receiving only usual care.

Aim 2 (Secondary): To determine if MTMs provided for up to 10 weeks after hospital discharge for patients with heart failure, diabetes mellitus or chronic kidney disease will reduce the risks of 90-day admissions for heart failure, admissions for diabetes-related complications, all-cause emergency department visits, all-cause death, and a composite of all-cause health care utilization and death.

Hypothesis 2: Patients receiving MTMs will have better clinical outcomes compared with patients who are receiving only usual care.

KP NOURISH Study Protocol Version 1.0

Aim 3 (Secondary): To determine if MTMs provided for up to 10 weeks after hospital discharge for patients with heart failure, diabetes mellitus or chronic kidney disease will experience improved selected patient-reported outcomes (i.e., self-efficacy, social isolation, patient satisfaction, and perceived caring) at 10 weeks post-discharge.

Hypothesis 3: Patients receiving MTMs will have better patient-reported outcomes compared with patients who receiving only usual care.

Aim 4 (Secondary): To determine if MTMs provided for up to 10 weeks with additional remotely delivered nutritional counseling after hospital discharge for patients with heart failure, diabetes mellitus or chronic kidney disease will experience improved all-cause and cause-specific clinical outcomes at 90-days post-discharge as well as selected patient-reported outcomes (i.e., self-efficacy, social isolation, patient satisfaction, and perceived caring) at 10-weeks post-discharge.

Hypothesis 4: Patients receiving MTMs with remotely delivered nutritional counseling will have lower 90-days risks of adverse clinical outcomes and better patient-reported outcomes at 10-weeks post-discharge than patients receiving MTMs alone.

[figure not shown]
6 Study Design

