10.4 Secondary Patient-reported Outcomes

The following scales will be used for targeted patient-reported outcomes:

- 1.) Change in perceived social isolation (Likert 1-5 scale: Never, Rarely, Sometimes, Often, Always)
 - a. I feel left out.
 - b. I feel that people barely know me.
 - c. I feel isolated from others.
 - d. I feel that people are around me but not with me.
- 2.) Change in perceived self-efficacy (i.e., "How confident are you that you can stick with healthful foods?" Likert 1-10 scale: ranging from Not Confident to Completely Confident)
 - a. Even if you need a long time to develop necessary routines?
 - b. Even if you have to try several times to make it work?
 - c. Even if you have to rethink your entire way of nutrition?
 - d. Even if you have to make a detailed plan?
- 3.) Change in perceived caring (i.e., "My current meals help to create a caring environment that helps me heal": Likert 1-5 scale: Strongly Disagree, Disagree, Neither Agree nor Disagree, Agree, Strongly Agree)

Responses to survey questions will be collected at baseline by phone and at the 10week follow-up phone call conducted by KPNC DOR research staff.

11 Supporting Documentation and Operational Considerations

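### Protocol 8.3 words the follow-up caring question and times the survey differently for the MTMs arms than 10.4, SAP 4.3 and the schedule do, and Aim 3 names a satisfaction comparison that cannot be made

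*Protocol*

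**What the plan says.** Protocol 10.4 and SAP 4.3 define the same patient-reported outcomes: four isolation questions, four self-efficacy questions, and one perceived-caring question, "My current meals help to create a caring environment that helps me heal". Neither gives a version specific to an arm. On collection, Protocol 10.4 says "Responses to survey questions will be collected at baseline by phone and at the 10week follow-up phone call". SAP 4.3 takes follow-up minus baseline for each question and compares MTMs with usual care by linear regression. SAP 3.1 limits this analysis to participants with both surveys.

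Protocol 8.3 lists what staff ask at follow-up, separately by arm:

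- Usual care: "Perceived caring related to diet (i.e., perception that current meals help create a caring environment that facilitates healing".
- MTMs arms: "Perceived caring (e.g., participating in a delivered MTMs program helps create a caring environment that facilitates healing".

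It also sets the time of the call separately:

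- Usual care: "KPNC DOR research staff will contact patients at 10-weeks after discharge from the index hospitalization".
- MTMs arms: "KPNC DOR research staff will contact patients after Ceres and POH have delivered their last meals" and the vendor has reported that service is complete. No day or window is given.

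Vendor satisfaction is listed for the MTMs arms only, and counseling satisfaction for the counseling arm only. The $10 gift card is mentioned for usual care only (Protocol 6 and 8.3).

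The schedule in Protocol 3 has a single follow-up column at discharge plus 70 days. Aim 3 (Protocol 5) covers "self-efficacy, social isolation, patient satisfaction, and perceived caring) at 10 weeks post-discharge", and Hypothesis 3 compares these outcomes with usual care.

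**The concern.** A change score needs the same question at both times, and a between-arm comparison needs the same question and the same timing in each arm. Section 8.3 departs from this in two ways. The MTMs arms appear to get a follow-up caring question about the meal program, which cannot have been asked in matching form at baseline because the baseline call takes place in hospital before any delivery (Protocol 6). Their survey date also depends on how deliveries went, whereas the usual-care date depends only on discharge. Separately, Aim 3 promises a comparison on satisfaction for which usual care supplies no data.

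At stake is the interpretation of secondary patient-reported outcomes. SAP 2 claims more than 80% power for even small differences on these, so a small artefact of measurement could also reach significance.

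**Working it through.** **1. Caring question, side by side.**

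| Place | Who and when | Subject of the question |
|---|---|---|
| Protocol 10.4 | all participants, baseline and follow-up | current meals |
| SAP 4.3 | all participants, baseline and follow-up | current meals |
| Protocol 8.3 | usual care, follow-up | current meals |
| Protocol 8.3 | MTMs arms, follow-up | taking part in the meal program |

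Under 10.4, each arm's change is meals question minus meals question. Under 8.3, the MTMs change becomes program question minus meals question. If δ is the true effect and w is the amount by which MTMs participants score the program wording above the meals wording, the expected contrast is δ + w, and the data cannot separate the two.

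Extent: 4 isolation + 4 self-efficacy + 1 caring = 9 questions analysed. One of nine is affected by wording, although it is the only question for its construct. Both MTMs arms have the same list entry and the same trigger, so the comparison between them is not made unlike by this.

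**2. Timing.** Inputs are weekly deliveries for ten weeks (Protocol 3 and 8.2.1), first delivery no later than one week after discharge (8.2.1), and a permitted pause of up to two consecutive weeks (8.2.2). I assume exactly ten deliveries, the first on day 1 to 7.

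- Last delivery = first day + 9 × 7 = first day + 63.
- No pause: 1 + 63 = day 64 to 7 + 63 = day 70. Against day 70, this is −6 to 0 days.
- A 14-day pause that is made up: day 78 to 84, or +8 to +14 days. The protocol does not say that paused weeks are made up.

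Time for vendor notice and for reaching the participant is added to each figure. Protocol 6 gives two further rules for those assigned to MTMs. Those unable to receive meals are surveyed at 10 weeks after discharge, and those receiving meals are surveyed once 10 weeks are complete and the last meal has been delivered. With 8.3, that makes three descriptions of the trigger for participants assigned to MTMs.

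**3. Satisfaction.** It is named in Aim 3, not listed for usual care in 8.3, and absent from both 10.4 and SAP 4.3. There is therefore neither a comparator measurement nor a planned analysis.

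**4. Sensitivity to an artefact.** SAP 2 gives no difference or SD for these outcomes, so its power claim can only be checked for consistency. With two-sided α = 0.05 and 80% power, the detectable difference is (1.960 + 0.842) × √(2/n) SD:

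- n = 1000 per arm: 2.802 × 0.0447 = 0.125 SD.
- n = 500 per arm: 2.802 × 0.0632 = 0.177 SD.

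The claim is consistent if small means about 0.2 SD, where power is 99.4% and 88.5%.

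Now set the true effect to zero and assume a shift of b SD in one arm. With t = b/√(2/n), the rejection rate is Φ(t − 1.960) + Φ(−t − 1.960):

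| Assumed shift b | 1000 per arm | 600 completers per arm |
|---|---|---|
| 0 | 5% | 5% |
| 0.02 SD | 7% | 6% |
| 0.05 SD | 20% | 14% |
| 0.10 SD | 61% | 41% |

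The values of b and the 600 completers are assumptions. The documents give no basis for a particular size.

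**The case against.** The strongest reply is that Protocol 10.4 and SAP 4.3 define what is analysed, and they give one caring question for everyone. Section 8.3 lists topics and is not a script. Its MTMs entry is offered as an example, and the survey form is not in the documents. This stands: a reader might infer that the MTMs arms were certainly asked a different question, and the text does not establish that. It does leave whoever writes the script with two conflicting instructions.

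On timing, the reply is that Protocol 3 sets day 70 for all, Protocol 8.2.1 puts the last delivery at the end of 10 weeks, and Protocol 6 requires 10 weeks to be complete before participants receiving meals are called. This also largely stands. A reader might infer from 8.3 that participants who stop meals early are surveyed much earlier than usual care, but Section 6 speaks against it. The late end of the range depends on paused weeks being made up, and descriptions of the service as lasting up to 10 weeks do not suggest an extension. What remains is a trigger tied to delivery, with no stated window, in the MTMs arms only.

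Vendor satisfaction can only be asked of people who used the vendor, so asking it in the MTMs arms alone is not a flaw. The fault lies in Aim 3 naming it against usual care.

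The usual-care-only gift card might be read as a further difference in measurement. It is not one: it does not alter any question, and 8.3 has staff mention it once the survey is done. It could affect who responds, which has some relevance because only completers are analysed, but the documents do not show whether participants knew of it beforehand.

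**Conclusion.** The point holds as a set of internal conflicts that are cheap to resolve. On caring, 8.3 contradicts 10.4 and SAP 4.3. Following 8.3 would make one of nine analysed questions non-comparable, both between arms and from baseline to follow-up. On timing, 8.3 departs from Aim 3 and the day-70 schedule, by about a week or less without pauses and by up to about two weeks if a two-week pause is made up, before any time for vendor notice and contact. The satisfaction part of Hypothesis 3 cannot be tested.

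The broader reading, that Aim 3 as a whole compares unlike measurements, is not supported. Self-efficacy and isolation have the same questions in every arm, and no document suggests that a timing gap of this size would shift the answers. The false-positive rates above show what an artefact could do if it existed, and rest on assumed shifts. The primary outcome is taken from the health record and is unaffected.

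**What to change.** - **Caring:** use the 10.4 question verbatim at baseline and follow-up in all three arms, and amend 8.3 to match. Any program-worded question should be a separate item for the MTMs arms only, outside the comparison with usual care.
- **Timing:** anchor the survey at day 70 after discharge with the same stated window in all arms, regardless of deliveries, and bring Protocol 6 and 8.3 into line with the schedule.
- **Satisfaction:** remove it from the Aim 3 and Hypothesis 3 comparison with usual care, and report it descriptively in the MTMs arms.
- **Response:** report survey response by arm. The gift card calls for nothing more than this.

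If calls have already been made, confirm which caring question was used and report the day of the call by arm.

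The cost is call-script and protocol wording, with no change in sample size. The downside of a fixed day is that some MTMs participants will be surveyed while still receiving meals.
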